7.3 Expedited Adverse Event Reporting

7.3.1 Expedited AE reporting for this study must be reported to the FDA/IRB and Genentech within 24 hours of awareness of the event. These requirements are briefly outlined in the tables below (Section 7.3.2).

7.3.2 Expedited Reporting Guidelines

Use the protocol number and the protocol-specific patient ID assigned during trial registration on all reports.

Note: A death on study requires both routine and expedited reporting regardless of causality, unless as noted below. Attribution to treatment or other cause must be provided.

Death due to progressive disease should be reported as **Grade 5 "Neoplasms benign**, malignant and unspecified (incl cysts and polyps) - Other (Progressive Disease)" under the system organ class (SOC) of the same name. Evidence that the death was a manifestation of underlying disease (*e.g.*, radiological changes suggesting tumor growth or progression: clinical deterioration associated with a disease process) should be submitted.

Phase 1 and Early Phase 2 Studies: Expedited Reporting Requirements for Adverse Events that Occur on Studies under an IND/IDE within 30 Days of the Last Administration of the Investigational Agent/Intervention ^{1,2}

FDA REPORTING REQUIREMENTS FOR SERIOUS ADVERSE EVENTS (21 CFR Part 312)

NOTE: Investigators MUST immediately report ANY Serious Adverse Events, whether or not they are considered related to the investigational agent(s)/intervention (21 CFR 312.64)

An adverse event is considered serious if it results in **ANY** of the following outcomes:

- 1) Death
- 2) A life-threatening adverse event
- 3) An adverse event that results in inpatient hospitalization or prolongation of existing hospitalization for ≥ 24 hours
- 4) A persistent or significant incapacity or substantial disruption of the ability to conduct normal life functions
- 5) A congenital anomaly/birth defect.
- Important Medical Events (IME) that may not result in death, be life threatening, or require hospitalization may be considered serious when, based upon medical judgment, they may jeopardize the patient or subject and may require medical or surgical intervention to prevent one of the outcomes listed in this definition. (FDA, 21 CFR 312.32; ICH E2A and ICH E6).

ALL SERIOUS adverse events that meet the above criteria MUST be immediately reported to the Sponsoring IRB/FDA and Genentech within the timeframes detailed in the table below.

Hospitalization	Grade 1 and Grade 2 Timeframes	Grade 3-5 Timeframes			
Resulting in Hospitalization ≥ 24 hrs	10 Calendar Days	24-Hour 5 Calendar			
Not resulting in Hospitalization ≥ 24 hrs	Not required	Days			

Expedited AE reporting timelines are defined as:

- "24-Hour; 5 Calendar Days" The AE must initially be reported to the IRB/FDA and Genentech within 24 hours of learning of the AE, followed by a complete expedited report within 5 calendar days of the initial 24-hour report.
- "10 Calendar Days" A complete expedited report on the AE must be submitted within 10 calendar days of learning of the AE.

¹Serious adverse events that occur more than 30 days after the last administration of investigational agent/intervention and have an attribution of possible, probable, or definite require reporting as follows:

Expedited 24-hour notification followed by complete report within 5 calendar days for:

• All Grade 3, 4, and Grade 5 AEs

Expedited 10 calendar day reports for:

• Grade 2 AEs resulting in hospitalization or prolongation of hospitalization

7.4 Routine Adverse Event Reporting

All Adverse Events must be reported in routine study data submissions. ALL AEs are to be reported through ONCORE.

EXCHANGE OF SINGLE CASE REPORTS TO GENENTECH

[name] will be responsible for collecting all protocol-defined Adverse Events (AEs)/Serious Adverse Events (SAEs), pregnancy reports (including pregnancy occurring in the partner of a male study subject), other Special Situation reports, AESIs and Product Complaints with an AE where the patient has been exposed to the Product. The completed MedWatch form should be sent to the Genentech contact specified below. Transmission of these reports (initial and follow-up) will be either electronically via email or by fax and within the timelines specified below:

[contact]

Email: usds [contact]

All Product Complaints without an AE should call via:

PC [contact] (M-F: 5 am to 5 pm PST)

Transmission of these reports (initial and follow-up) will be either electronically or by fax and within the timelines specified below:

Serious Adverse Drug Reactions (SADRs)	15 calendar days of the awareness date						
Other SAEs	30 calendar days of the awareness date.						
Special Situation Reports (Pregnancy)	30 calendar days of the awareness date.						
	30 calendar days of the awareness date.						
Special Situation Reports (Other)	-						
Product Complaints	15 calendar days of the awareness date.						
AESIs	15 calendar days of the awareness date.						

Serious Adverse Drug Reactions (SADRs)

Serious AE reports that are related to the Product or where the causality is assessed as unknown or not provided shall be transmitted to Genentech within fifteen (15) calendar days of the awareness date.

Other SAEs

Serious AE reports that are unrelated to the Product shall be transmitted to Genentech within thirty (30) calendar days of the awareness date.

• Special Situation Reports

Pregnancy reports

While such reports are not serious AEs or Adverse Drug Reactions (ADRs) per se, as defined herein, any reports of pregnancy (including pregnancy occurring in the partner of a male study subject), where the fetus may have been exposed to the Product, shall be transmitted to Genetech within thirty (30) calendar days of the awareness date. Pregnancies will be followed-up until the outcome of the pregnancy is known, whenever possible, based upon due diligence taken to obtain the follow-up information.

Pregnancies in Female Partners of Male Patients

Male patients will be instructed through the Informed Consent Form to immediately inform the investigator if their partner becomes pregnant during the study or within 160 days after the last dose of study drug. A Clinical Trial Pregnancy Reporting Form should be completed and submitted to Genentech within thirty (30) calendar days of the awareness date.

o Other Special Situation Reports, as defined above, shall be transmitted to Genentech within thirty (30) calendar days of the awareness date.

• **Product Complaints**

All Product Complaints (with or without an AE) shall be forwarded to Genentech within fifteen (15) calendar days of the awareness date.

AESIs

AESIs requiring expedited reporting (related or possibly related to Genentech product or where the causality is assessed as unknown or not provided) shall be forwarded to Genentech within fifteen (15) calendar days of the awareness date. Others (non-related to Genentech product) shall be sent within thirty (30) calendar days.

Case Transmission Verification of Single Case Reports

The Sponsor agrees to conduct the Case Transmission verification to ensure that all single case reports have been adequately received by Genentech via [name] emailing Genentech a Quarterly line-listing documenting single case reports sent by [name] to Genentech in the preceding time period.

The periodic line-listing will be exchanged within seven (7) calendar days of the end of the agreed time period. Confirmation of receipt should be received within the time period mutually agreed upon.

If discrepancies are identified, the Sponsor and Genentech will cooperate in resolving the

discrepancies. The responsible individuals for each party shall handle the matter on a case-by-case basis until satisfactory resolution. The sponsor shall receive reconciliation guidance documents within the 'Activation Package'.

Following Case Transmission Verification, single case reports which have not been received by Genentech shall be forwarded by [name] to Genentech within five (5) calendar days from request by Genentech.

At the end of the study, a final cumulative Case Transmission Verification report will be sent to Genentech.

MEDWATCH 3500A REPORTING GUIDELINES

In addition to completing appropriate patient demographic (Section A) and suspect medication information (Section C & D), the report should include the following information within the Event Description (Section B.5) of the MedWatch 3500A form:

- Protocol number and title description
- Description of event, severity, treatment, and outcome if known
- Supportive laboratory results and diagnostics (Section B.6)
- Investigator's assessment of the relationship of the adverse event to each investigational product and suspect medication

Follow-Up Information

- Additional information may be added to a previously submitted report by any of the following methods:
- Adding to the original MedWatch 3500A report and submitting it as follow-up
- Adding supplemental summary information and submitting it as follow-up with the original MedWatch 3500A form
- Summarizing new information and faxing it with a cover letter including patient identifiers (i.e. D.O.B. initial, patient number), protocol description and number, if assigned, brief adverse event description, and notation that additional or follow-up information is being submitted (The patient identifiers are important so that the new information is added to the correct initial report)

MedWatch 3500A (Mandatory Reporting) form is available at https://www.fda.gov/media/69876/download

8. REPORTING TO REGULATORY AUTHORITIES, ETHICS COMMITTEES AND INVESTIGATORS

Genentech as the Marketing Authorization Holder will be responsible for the reporting of individual case safety reports from the study to the regulatory authority in compliance with applicable regulations.

[name] will be responsible for the expedited reporting of safety reports originating from the Study to the Ethics Committees and Institutional Review Boards (IRB), where applicable.

[name], as the Sponsor of the Study, will be responsible for the expedited reporting of safety reports originating from the Study to the EMA through Eudravigilance Clinical Trial Module (EVCTM).

[name] will be responsible for the distribution of safety information to its own investigators, where relevant, in accordance with local regulations.

[name] will be responsible for the distribution of safety information to Emory IRB:

Emory IRB [name] [contact] [contact]

For questions related to safety reporting, please contact Genentech Drug Safety:

[contact]

[contact] or [contact]

Other REPORTS

Investigator will forward a copy of the Publication to Genentech upon completion of the Study.

8.1 Secondary Malignancy

A *secondary malignancy* is a cancer caused by treatment for a previous malignancy (*e.g.*, treatment with investigational agent/intervention, radiation or chemotherapy). A secondary malignancy is not considered a metastasis of the initial neoplasm.

All secondary malignancies that occur following treatment with an agent under an IND/IDE must be reported through **ONCORE**. Three options are available to describe the event:

- Leukemia secondary to oncology chemotherapy (e.g., acute myelocytic leukemia [AML])
- Myelodysplastic syndrome (MDS)
- Treatment-related secondary malignancy

Any malignancy possibly related to cancer treatment (including AML/MDS) should also be reported via the routine reporting mechanisms outlined in each protocol.

8.2 Second Malignancy

A second malignancy is one unrelated to the treatment of a prior malignancy (and is **NOT** a metastasis from the initial malignancy).

STUDY CLOSE-OUT

Any study report submitted to the FDA by the Sponsor-Investigator should be copied to Genentech. This includes all IND annual reports and the Clinical Study Report (final study report). Additionally, any literature articles that are a result of the study should be sent to Genentech. Copies of such reports should be mailed to the assigned Clinical Operations contact for the study:

[Clinical Operations Contact Information

l [contact]

And to Genentech Drug Safety CTV oversight mail box at: ctvist [contact]

QUERIES

Queries related to the Study will be answered by the [name] or study staff. However, responses to all safety queries from regulatory authorities or for publications will be discussed and coordinated between the Parties. The Parties agree that Genentech shall have the final say and control over safety queries relating to the Product. [name] agrees that it shall not answer such queries from regulatory authorities and other sources relating to the Product independently but shall redirect such queries to Genentech.

Both Parties will use all reasonable effort to ensure that deadlines for responses to urgent requests for information or review of data are met. The Parties will clearly indicate on the request the reason for urgency and the date by which a response is required.

SAFETY CRISIS MANAGEMENT

In case of a safety crisis, e.g., where safety issues have a potential impact on the indication(s), on the conduct of the Study, may lead to labeling changes or regulatory actions that limit or restrict the way in which the Product is used, or where there is media involvement, the Party where the crisis originates will contact the other Party as soon as possible.

The Parties agree that Genentech shall have the final say and control over safety crisis management issues relating to the Product. [name] agrees that it shall not answer such queries from media and other sources relating to the Product but shall redirect such queries to Genentech.

COMPLIANCE WITH PHARMACOVIGILANCE AGREEMENT / AUDIT

The Parties shall follow their own procedures for adherence to AE reporting timelines.

Each Party shall monitor and, as applicable, request feedback from the other Party regarding AE report timeliness in accordance with its own procedures. The Parties agree to provide written responses in a timely manner to inquiries from the other Party regarding AE reports received outside the agreed upon Agreement timelines. If there is any detection of trends of increasing or persistent non-compliance to transmission timelines stipulated in this Agreement, both Parties agree to conduct ad hoc or institute a regular joint meeting to address the issue.

In case of concerns related to non-compliance of processes, other than exchange timelines, with this Agreement, the Parties will jointly discuss and collaborate on clarifying and resolving the issues causing non-compliance. Every effort will be made by the non-compliant Party to solve the non-compliance issues and inform the other Party of the corrective and preventative actions taken.

Upon justified request, given sufficient notice of no less than sixty (60) calendar days, an audit under the provisions of this Agreement can be requested by either Party. The Parties will then discuss and agree in good faith upon the audit scope, agenda and execution of the audit. The requesting Party will bear the cost of the audit.

How to file a complaint?

For all Investigator Initiated Studies (interventional and non-interventional):

• For Non-Interventional Investigator Initiated Studies: [contact]

9. PHARMACEUTICAL INFORMATION

A list of the adverse events and potential risks associated with the investigational or commercial agents administered in this study can be found in Section 7.1.

9.1 Investigational Agent(s)

Rituxan Hycela:

Mechanism of Action

Rituximab is a monoclonal antibody that targets the CD20 antigen expressed on the surface of pre-B and mature B-lymphocytes. Upon binding to CD20, rituximab mediates B-cell lysis. Possible mechanisms of cell lysis include complement dependent cytotoxicity (CDC) and antibody dependent cell mediated cytotoxicity (ADCC). Hyaluronan is a polysaccharide found in the extracellular matrix of the subcutaneous tissue. It is depolymerized by the naturally occurring enzyme hyaluronidase. Unlike the stable structural components of the interstitial matrix, hyaluronan has a half-life of approximately 0.5 days. Hyaluronidase human increases permeability of the subcutaneous tissue by temporarily depolymerizing hyaluronan. In the doses administered, hyaluronidase human in RITUXAN HYCELA acts locally.

The effects of hyaluronidase human are reversible and permeability of the subcutaneous tissue is restored within 24 to 48 hours.

Version Date: 04-05-2021 v6.0

Hyaluronidase human has been shown to increase the absorption rate of a rituximab product into the systemic circulation when given in the subcutis of Göttingen Minipigs.

Rituxan Hycela is given IV Rituximab as first dose followed by rituxan hycela subcutaneously for subsequent doses for those without severe infusion reactions.

DESCRIPTION

RITUXAN HYCELA is a combination of rituximab and hyaluronidase human. Rituximab is a genetically engineered chimeric murine/human monoclonal IgG1 kappa antibody directed against the CD20 antigen. Rituximab has an approximate molecular weight of 145 kD. Rituximab has a binding affinity for the CD20 antigen of approximately 8.0 nM. Rituximab is produced by mammalian cell (Chinese Hamster Ovary) suspension culture in a nutrient medium that may contain the antibiotic gentamicin. Gentamicin is not detectable in the final product. Recombinant human hyaluronidase is an endoglycosidase used to increase the dispersion and absorption of co-administered drugs when administered subcutaneously. It is produced by mammalian (Chinese Hamster Ovary) cells containing a DNA plasmid encoding for a soluble fragment of human hyaluronidase (PH20). It is a glycosylated single-chain protein with an approximate molecular weight of 61 kD.

RITUXAN HYCELA (rituximab and hyaluronidase human) Injection is a colorless to yellowish, clear to opalescent solution supplied in sterile, preservative-free, single-dose vials for subcutaneous administration.

RITUXAN HYCELA is supplied as 1,400 mg rituximab and 23,400 Units hyaluronidase human per 11.7 mL in single-dose vials or 1,600 mg rituximab and 26,800 Units hyaluronidase human per 13.4 mL in single-dose vials. Each mL of solution contains rituximab (120 mg), hyaluronidase human (2,000 Units), L-histidine (0.53 mg), L-histidine hydrochloride monohydrate (3.47 mg), L-methionine (1.49 mg), polysorbate 80 (0.6 mg), α,α-trehalose dihydrate (79.45 mg), and Water for Injection.

9.1.1 Agent Ordering and Agent Accountability

- 9.1.1.1 Rituxan be requested by the Principal Investigator (or their authorized designee) at Emory.
- 9.1.1.2 Agent Inventory Records The investigator, or a responsible party designated by the investigator, will maintain a careful record of the inventory and disposition of all agents

9.2 Commercial Agent(s)

The following commercial agents used to treat melanoma will be utilized as part of standard of care. Please refer to the manufacturer package insert for details.

Nivolumab, commercial supply.

Preparation for Administration

Visually inspect drug product solution for particulate matter and discoloration prior to administration. Nivolumab is a clear to opalescent, colorless to pale-yellow solution. Discard the vial if the solution is cloudy, discolored, or contains extraneous particulate matter other than a few translucent-to-white, proteinaceous particles. Do not shake the vial.

- Withdraw the required volume of nivolumab and transfer into an intravenous container.
- Dilute nivolumab with either 0.9% Sodium Chloride Injection, USP or 5% Dextrose Injection, USP to prepare an infusion with a final concentration ranging from 1 mg/mL to 10 mg/mL.
- Mix diluted solution by gentle inversion. Do not shake.
- Discard partially used vials or empty vials of nivolumab.

Storage of Infusion

The product does not contain a preservative. After preparation, store the nivolumab infusion either:

- at room temperature for no more than 4 hours from the time of preparation. This includes room temperature storage of the infusion in the IV container and time for administration of the infusion or
- under refrigeration at 2°C to 8°C (36°F to 46°F) for no more than 24 hours from the time of infusion preparation. Do not freeze.

Administration

Administer the infusion over 30 minutes through an intravenous line containing a sterile, non-pyrogenic, low protein binding in-line filter (pore size of 0.2 micrometer to 1.2 micrometer). Do not coadminister other drugs through the same intravenous line. Flush the intravenous line at end of infusion.

Dosage forms

Injection: 40 mg/4 mL (10 mg/mL) and 100 mg/10 mL (10 mg/mL) and 240 mg/24mL (10 mg/mL) solution

Ipilimumab, commercial supply.

Preparation for administration

Do not shake product.

- Inspect parenteral drug products visually for particulate matter and discoloration prior to administration. Discard vial if solution is cloudy, there is pronounced discoloration (solution may have pale-yellow color), or there is foreign particulate matter other than translucent-to-white, amorphous particles.
- Allow the vials to stand at room temperature for approximately 5 minutes prior to preparation of infusion.
- Withdraw the required volume of ipilimumab and transfer into an intravenous bag.
- Dilute with 0.9% Sodium Chloride Injection, USP or 5% Dextrose Injection, USP to prepare a diluted solution with a final concentration ranging from 1 mg/mL to 2 mg/mL. Mix diluted solution by gentle inversion.

Storage of infusion

- Store the diluted solution for no more than 24 hours under refrigeration (2°C to 8°C, 36°F to 46°F) or at room temperature (20°C to 25°C, 68°F to 77°F).
- Discard partially used vials or empty vials of ipilimumab.

Administration Instructions

- Do not mix ipilimumab with, or administer as an infusion with, other medicinal products.
- Flush the intravenous line with 0.9% Sodium Chloride Injection, USP or 5% Dextrose Injection, USP after each dose.
- Administer diluted solution over 90 minutes through an intravenous line containing a sterile, non-pyrogenic, low-protein-binding in-line filter.

Dosage forms

Injection: 50 mg/10 mL (5 mg/mL) Injection: 200 mg/40 mL (5 mg/mL)

10. BIOMARKER, CORRELATIVE, AND SPECIAL STUDIES

This protocol involves extensive correlative studies to gain fundamental insights into the effects of B cell depletion in the setting of immune checkpoint blockade.

Specimens:

Both blood and tissue specimens will be analyzed.

Time-points:

Pre and Post treatment tissue samples

Pre and Post-treatment peripheral blood mononuclear cells.

Assays:

Mass cytometry.

Gene expression, including single cell sequencing.

B and T cell receptor sequencing

Functional assays

Immunohistochemistry

Change cycle below to show nivo being administered on week 13

10.1 Laboratory Correlative Studies

- 10.1.1 Title Peripheral Blood for immune analysis to be drawn any time prior to the cycle of treatment as long as it's the same day as treatment
- 10.1.1.1 Collection of Specimen(s): collect 40-60 ml in green top heparin anticoagulant.
- 10.1.1.2 Handling of Specimens(s): keep at room temperature.
- 10.1.1.3 Shipping of Specimen(s): call [name] lab for pickup.
- 10.1.1.4 Site(s) Performing Correlative Study; [name] lab

10.1.2 *Title – Tissue for immune analysis*

- 10.1.2.1 Collection of Specimen(s): Fresh tissue from operating room
- 10.1.2.2 Handling of Specimens(s): keep at room temperature.
- 10.1.2.3 Shipping of Specimen(s): call [name] lab for pickup.
- 10.1.2.4 Site(s) Performing Correlative Study: [name] lab.

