1.2 Secondary Objectives

- To evaluate the safety and tolerability (in terms of Rituxan-related adverse events) in patients with melanoma receiving CCB.
- To compare objective response rate in patients receiving CCB therapy + Rituxan versus CCB therapy alone.
- To compare 1 year overall and progression-free survival in patients receiving CCB therapy + Rituxan versus CCB therapy alone.
- To compare changes in CD21^{lo} B cells in patients receiving CCB therapy + Rituxan versus CCB therapy alone.
- To compare changes in T cells in patients receiving CCB therapy + Rituxan versus CCB therapy alone.

Exploratory Objectives

• To compare treatment induced changes in tumor tissue in patients receiving CCB therapy + Rituxan versus CCB therapy alone.

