2.3 Rationale

Immune related adverse events (IRAEs) as a limiting toxicity of combination checkpoint blockade:

Blockade of T cell immune checkpoints PD-1/PD-L1 and CTLA-4 has emerged as an effective therapy for melanoma(1-4). Immune checkpoint blockade with monotherapy (anti-CTLA4 or anti-PD-1 alone) leads to tumor regression in only a subset of patients and combination therapy has therefore, been explored as a strategy to enhance clinical efficacy. The best studied combination therapy (concurrent administration of PD-1 and CTLA-4 blockade) leads to high response rates in advanced melanoma(5-10). However, increase in tumor regressions following combination therapy is associated with a marked increase in Grade 3 and 4 IRAEs resulting in significant morbidity and discontinuation of therapy in up to one third of patients(11, 12). Reduction in antibody dosages may be one way to partly reduce the risk for IRAEs with combination therapy, however the impact of such strategy on clinical efficacy remains to be resolved(13). There remains an urgent need to better understand the pathogenesis of IRAEs following CCB therapy and how/whether they can be prevented. Ability to prevent these IRAEs will have a major impact on the applicability of combination immune checkpoint blockade as therapy in melanoma as well as other cancers. This is not just because of short-and long-term morbidity and costs associated with IRAEs, but also because IRAEs often prevent delivery of planned therapy in several patients.

Importance of human studies to test biomarkers and prevention of IRAEs following checkpoint blockade:

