5. TREATMENT PLAN

5.1 Agent Administration

Once the investigator has signed the eligibility checklist, randomization may proceed. Patients meeting study entry criteria will be randomized to treatment ARM A or Arm B by the study statistician, [name]. Eligible subjects (eligibility confirmed and checklist signed) will be assigned to a treatment arm until 44 subjects (22 in each arm) have been enrolled. The study coordinator will update Oncore and ERMS reflect randomization information.

Following randomization, patients should begin protocol treatment within 5 business days. Issues that would cause treatment delays should be discussed with the Principal Investigator.

Treatment will be administered on an *outpatient* basis. Reported adverse events and potential risks are described in Section 7. Appropriate dose modifications are described in Section 6. No investigational or commercial agents or therapies other than those described below may be administered with the intent to treat the patient's malignancy.

Patients will be randomly assigned 1:1 using block randomization with a block of 6 patients. Randomization schema will be kept in the research pharmacy.

Patients with unresectable stage III or stage IV melanoma being treated with FDA approved standard of care immune checkpoint combination therapy with Ipilimumab and Nivolumab are eligible for this trial.

Patients will be randomized 1:1 to either continue therapy with standard of care Ipilimumab and Nivolumab (ARM A) or standard of care Ipilimumab and Nivolumab plus **4 doses of weekly Rituxan** (ARM B).

Patients enrolling on this study following treatment failure on single agent anti-PD-1 will be distributed equally between arms A and B of the study.

Induction Phase:

ARM A: Cycles 1-4

Each cycle is 21 days and includes Ipilimumab (3 mg/kg) on day 1 plus Nivolumab (1 mg/kg) on Day 1.

ARM B. Cycles 1-4

Each cycle is 21 days and includes Ipilimumab (3 mg/kg) on day 1 plus Nivolumab (1 mg/kg) on

Version Date: 04-05-2021 v6.0

Day 1. In addition, patients will receive 4 weekly doses of Rituxan (first dose 375 mg/m2 IV and then 3 weekly doses of 1400 mg Rituxan Hycela subcutaneous, as per current label for Rituxan Hycela).

First dose of Rituxan will be administered 1 week after start of Ipi/Nivolumab therapy. 3rd dose of Rituxan will be administered on day 2 of cycle 2 after infusion of Ipi/Nivo on week4.

Continuation Phase:

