11. STUDY CALENDAR

Schedules shown in the Study Calendar below are provided as an example and should be modified as appropriate.

Baseline evaluations are to be conducted within 3 weeks prior to start of protocol therapy. Scans and x-rays must be done \leq 4 weeks prior to the start of therapy. In the event that the patient's condition is deteriorating, laboratory evaluations should be repeated within 48 hours prior to initiation of the next cycle of therapy.

All protocol visits have a plus or minus 3 business day window.

Rituxan should be given after ipi/nivo infusion for subjects on Arm B. The timing of Rituxan is 1-2 days (preferably 1 day) following ipi-nivo infusion.

		1	ı	ı						1	1					
	Pre- Study	Wk 1	Wk 2	Wk 3	Wk 4	Wk 5	Wk	Wk	Wk 8	Wk 9	Wk 10	WK 12	Wk 13	WK 17	WK 21	Off Study
IPI 3mg/kg + Nivo 1mg/kg		X			X			X			X					
Nivo 480mg IV ^a													X	X	X	
Rituxan IV (loading dose)			X													
Rituxan SQ				X	X	X										
Informed consent	X															
Demographics	X															
Medical history	X															
Con Medications	X	X	X	X	X			X			X		X	X	X	X
Physical exam	X	X			X			X			X		X	X	X	X
Vital signs	X	X	X	X	X			X			X		X	X	X	X
Height	X															
Weight	X	X	X	X	X			X			X		X	X	X	X
Performance status	X	X			X			X			X		X			X
CBC w/diff, plts	X	X	X	X	X			X			X		X	X	X	X
Serum chemistry with LDH	X	X	X	X	X			X			X		X	X	X	X
EKG (12-lead)	X															
Adverse Event	X	X	X	X	X			X			X		X	X	X	X
Radiologic Evaluation ^b	X											X				
B-HCG	X															
Hepatitis B (HepB surface antigen and HepB core antibody), Hep C and HIV serology	X															
TSH, Free T, ACTH, cortisol	X				X			X			X		X	X	X	X
Blood correlative	X		X		X						X		X			X
Fresh Tissue Biopsy ^c	X				X											

^a given every 4 weeks starting at Week 13 for up to 13 doses.

^b CT scans n/c/a/p with contrast every 12 weeks for the first two years, then every 6 months for five years. MRI brain with contrast should be done at baseline, then every 6 months for patients with no history of CNS mets as per standard of care; every 3 months for those with a history of CNS metastases for two years, then every 6 months. CT head can be used for patients with a contraindication to MRI.

^C Tissue biopsy before week 4 is optional but encouraged whenever possible.

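### Section 10.1.1 ties correlative blood to treatment days, which conflicts with the calendar and may make samples missing unequally by arm and in relation to toxicity

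*Combined protocol and SAP*

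**What the plan says.** The title line of Section 10.1.1 says that peripheral blood for immune analysis is "to be drawn any time prior to the cycle of" treatment, "as long as it's the same day as treatment". Apart from the general pre- and post-treatment time points in Section 10, this is the only timing rule in that section.

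The Section 11 calendar has one row, "Blood correlative", not split by arm. It is marked at pre-study, weeks 2, 4, 10 and 13, and off study. In the same grid, ipilimumab plus nivolumab falls at weeks 1, 4, 7 and 10, and nivolumab 480 mg starts at week 13. The only week-2 treatment is in the row that begins "Rituxan IV (loading dose", which concerns Arm B. The calendar introduces itself with the sentence "Schedules shown in the Study Calendar below are provided as an example and should be modified as appropriate".

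Two of the five secondary objectives in Section 1.2 use these samples. One concerns CD21lo B cells; the other reads "To compare changes in T cells in patients receiving CCB therapy + Rituxan versus CCB therapy alone". Section 14 gives neither of them an endpoint, time point, analysis method or rule for missing samples.

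Section 2.3 describes grade 3 and 4 IRAEs on the combination as "resulting in significant morbidity and discontinuation of therapy in up to one third of patients". It also says that early B-cell changes correlated with the development and severity of IRAEs and came several weeks before them.

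**The concern.** The two texts on when to draw blood cannot both be followed at every marked visit. A site that applies Section 10.1.1 as written has no treatment day in Arm A at week 2, and none at week 10 or 13 for a patient whose ipilimumab and nivolumab have been stopped. A calendar that calls itself an example does not settle which text governs.

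Stopping is linked to IRAEs, which are the primary outcome and are expected to be three times as frequent in Arm A. Samples lost this way would not be a random subset. They would be missing more often in the control arm, and among patients in whom the rationale expects the largest B-cell change. A comparison at week 10 or 13 could then be restricted to patients who tolerated treatment, and the early comparison could lack its control group. Blood that was not drawn cannot be recovered at the analysis stage.

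**Working it through.** **1. Scheduled draws against dosing days (Section 11 grid)**

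| Draw | Arm A dose | Arm B dose | Meets the same-day condition |
|---|---|---|---|
| Pre-study | none | none | neither arm |
| Week 2 | none | Rituxan | Arm B only |
| Week 4 | ipi/nivo | ipi/nivo, with Rituxan that week | both, if still dosed |
| Week 10 | ipi/nivo | ipi/nivo | both, if still dosed |
| Week 13 | nivolumab | nivolumab | both, if still dosed |
| Off study | none | none | neither arm |

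Under the literal rule, week 2 yields 0 of 22 samples in Arm A and up to 22 of 22 in Arm B.

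**2. The plan's own figure.** Section 14.2 states about 80% power for 60% versus 20% with 22 per arm, using Fisher's exact test at one-sided 0.05. Exact enumeration gives 79.1%, so the figure is reproduced. The plan states no figure for the correlative comparisons. The 60% and 20% rates are used here only to show how losses could differ by arm.

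**3. Samples lost at weeks 10 and 13.** Let p be the grade 3 or greater IRAE rate (0.60 in Arm A, 0.20 in Arm B) and q the share of those patients who are off treatment by the draw. The documents do not give q, so it is an assumption, shown over a range.

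- Samples lost = 22pq; samples left = 22(1 − pq).
- IRAE share among those sampled = p(1 − q)/(1 − pq).
- Illustrative contrast = Arm A share minus Arm B share. This assumes that the marker is 1 unit higher in patients with such an IRAE and that the arm has no other effect. With complete sampling it is 0.60 − 0.20 = 0.40.

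Example at q = 50%: Arm A 0.30/0.70 = 0.429; Arm B 0.10/0.90 = 0.111; contrast 0.32.

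| q | Arm A lost / left | Arm B lost / left | IRAE share sampled, A / B | Contrast | Shrinkage |
|---|---|---|---|---|---|
| 25% | 3.3 / 18.7 | 1.1 / 20.9 | 53% / 16% | 0.37 | 7% |
| 50% | 6.6 / 15.4 | 2.2 / 19.8 | 43% / 11% | 0.32 | 21% |
| 56% | 7.3 / 14.7 | 2.4 / 19.6 | 40% / 10% | 0.30 | 25% |
| 75% | 9.9 / 12.1 | 3.3 / 18.7 | 27% / 6% | 0.21 | 47% |

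The 56% row takes the background figure of up to one third stopping, places all of it on Arm A's IRAE patients before the draw, and solves 0.60q = 1/3. The 75% row implies that 45% of Arm A stops (0.75 × 60%), which is more than that background figure.

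**4. Sensitivity to a direct drug effect.** Section 9.1 says that rituximab lyses B cells, which step 3 ignores. Adding an assumed direct effect of 1 unit in the same direction, the contrast goes from 1.40 to 1.32 at q = 50% (6% smaller) and from 1.40 to 1.21 at q = 75% (13% smaller). The relative shrinkage therefore depends heavily on an effect whose size the documents do not give.

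**5. Position of the Arm B week-2 sample.** Section 5.1 states "First dose of Rituxan will be administered 1 week after start of Ipi/Nivolumab therapy", and the calendar grid agrees. The Schema, and on its face the text above the calendar, put Rituxan 1 to 2 days after ipilimumab and nivolumab. Under the first schedule a pre-dose week-2 sample precedes all Rituxan; under the second it follows the first dose. Arm A has no week-2 dose under either.

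**The case against.** The strongest reply is that Section 10.1.1 is simply a pre-dose rule for draws that fall on dosing visits. The calendar schedules pre-study and off-study draws that cannot be on treatment days, and it marks week 2 for both arms alongside laboratory tests and an adverse-event check. On that reading Arm A is sampled at week 2. This reading is available, but Section 10.1.1 does not say it, and the modifiable calendar does not impose it. The conflict stands.

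Second, no passage forbids sampling a patient who has stopped, the off-study draw gives a later sample, and a patient who stops ipilimumab may still receive nivolumab at week 13. All true. Equally, no passage requires the draw, and an off-study sample comes at a variable time that does not match week 10 or 13.

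Third, Sections 5.2 to 5.4 remove patients for unacceptable adverse events and follow them for 4 weeks, or until the event resolves or stabilises, so visits could end whatever Section 10.1.1 says. This stands, and it means that rewording Section 10.1.1 alone is not enough.

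Fourth, the rationale points to early B-cell changes. Week 4 is affected only in patients who stop before the second dose, and no week-10 or week-13 analysis is specified. The 60% rate also covers 6 months, so some events may follow week 13. These points limit the likely size of any bias. They do not help week 2, which is also an early sample.

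**Conclusion.** The point holds as a conflict between Sections 10.1.1 and 11 that puts two secondary comparisons at avoidable risk, and it should be fixed. The week-2 gap in Arm A (0 of 22) follows from the literal wording alone. The dependence of weeks 10 and 13 on continued dosing also follows from that wording. That the losses would be unequal and informative rests on the plan's 60% and 20% rates and on the stated link between IRAEs and stopping.

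A reader might infer more: that the protocol prohibits sampling off treatment, that patients who stop will certainly lose their later samples, and that the comparisons are therefore biased by a known amount. The documents do not support this. The supportable statement is that the wording may bias these comparisons. The illustrative shrinkage runs from 7% at q = 25% to 25% at q of about 56%. It is smaller if Rituxan acts directly on the marker in the same direction, as assumed in step 4. None of these percentages is an estimate, because neither q nor the marker difference is given.

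**What to change.** Reword Section 10.1.1 along these lines: *draw at calendar weeks 2, 4, 10 and 13 in both arms, whether or not treatment is given or has been stopped, as long as the patient remains in follow-up; when a dose is given that day, draw before dosing.* State that the week-2 draw applies to Arm A. Align Sections 5.2 to 5.4 so that these draws still apply after treatment stops.

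Separately, reconcile the Schema and the Section 11 text with Section 5.1 and the calendar grid on the timing of the first Rituxan dose, then state whether the Arm B week-2 sample falls before or after it.

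Moving the baseline draw to the first treatment day and deleting the sentence that calls the calendar an example are optional.

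The cost is wording in a few sections, with no time point added. Patients off treatment would need blood taken at a clinic visit, and Arm A would attend at week 2, where the calendar already marks laboratory tests. Before deaths, withdrawals and other ends of follow-up, the planned number becomes 22 versus 22 at each of the four weeks.
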